## 12.5.2 Safety objectives

### 12.5.2.1 Analysis set and grouping for the analyses

For all safety analyses, the safety set will be used. All listings and tables will be presented by treatment received.

The overall observation period will be divided into three mutually exclusive segments:

- pre-treatment period: from day of patient's informed consent to the day before first dose of study medication
- on-treatment period: from day of first dose of study medication to last dose of study medication and up to 30 days after last dose.
- Post-treatment period: starting at day 31 after last administration of study treatment (MBG453 or HMA)
- Note : for patients who discontinue MBG453 investigational study treatment to receive transplant, they will not be included in the safety set (post discontinuation) and only be followed up for [REDACTED] transplant related mortality.

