### **12.1.2 Safety Set (SS)**

The Safety Set includes all patients who received at least one dose of study medication..

[REDACTED]

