## 12.4 Analysis of the primary endpoint

### 12.4.1 Definition of primary endpoint

Primary objective is to assess the safety profile of MBG453 (sabatolimab) 800 mg (every 4 weeks) given in combination with HMAs (IV/SC/ Oral) by 12 months. For all primary safety analyses, the Safety Set will be used, unless stated otherwise. Additionally, safety profile will be assessed beyond the primary time point until the end of the study.

The variables for the primary analysis are incidence and severity of AEs and SAEs, and changes in laboratory values and vital signs.

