The analysis described here will be conducted by), Novartis, using statistical software SAS® Version 9.4 according to the Statistical methods and data analysis Section 12 of the study protocol which will be available in Appendix 16.1.1 of the CSR. Important information will be given in the following sections and further details are provided, as applicable, in the Appendix 16.1.9 of the CSR.

Unless otherwise specified, the statistical methodologies including the analysis sets, analysis models, algorithms, and conventions are following the Oncology study amended protocol CMBG4531US01 version 02.

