1.1 Study design

This is a single-arm, non-randomized, open label, phase II multi-center study of intravenous MBG453 (Sabatolimab) added to FDA approved HMAs of investigator's choice (IV/SC/ Oral) in adult subjects with intermediate, high or very high risk myelodysplastic syndrome (MDS) as per IPSS-R criteria.

Study treatment will be administered for 12 months within the core phase of the study. After the 12 months core phase, subjects may enter the extension phase (based on investigator decision).

For subjects that will receive treatment in the extension phase, they are allowed to continue treatment with MBG453 only, HMA only or MBG453+HMA.

In addition, all subjects who discontinued (at core phase) study treatment (unless due to progression) may enter the extension phase. In the extension phase, subjects who discontinued study treatment due to reasons other than progression, death, lost to follow-up, or withdrawal of consent (i.e. transplantation, adverse events, etc.) will have hematology assessments, Patient Reported Outcomes (PRO) and response assessments at defined time points until documented disease progression, death, lost to follow-up, withdrawal of consent, or have reached the end of extension phase, whichever comes first. Subjects who progress on study [core phase (first 12 months) or extension phase (additional 12 months)] will enter the post treatment safety follow-up period.

Post treatment follow-up is for safety collection and is up to 150 days post core phase or extension phase discontinuation. Survival data will be collected until end of study inclusive of the extension and post treatment follow-up duration.

Subjects who become eligible for hematopoietic stem cell transplant (HSCT) or intensive chemotherapy at any time during the course of the study will be discontinued from study treatment. However, they may continue into the extension phase for safety.

The study treatment consists of cycles of MBG453 in combination with HMA administered to the subjects until treatment discontinuation as described in the protocol. The planned duration of a cycle is 28 days.

Planned number of subjects

Novartis has decided to permanently halt recruitment based on a re-evaluation of the development strategy for sabatolimab. Subjects who are currently on study treatment or in follow-up will be continued per the protocol.

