2.2 Analysis sets

The analysis sets to be used as defined below. The FAS will be used for efficacy analysis. The Safety Set will be used for all the safety analysis.

Full Analysis Set

The FAS comprises all enrolled subjects to whom took any component of the study treatment.

Safety Set

The Safety Set includes all subjects who received at least one dose of any component of the study treatment (MBG453 + HMA).

[REDACTED]

[REDACTED]

[REDACTED]

1. [REDACTED]

2. [REDACTED]

[REDACTED]

3. [REDACTED]

[REDACTED]

[REDACTED]

[REDACTED]

Subject Classification

Subjects may be excluded from the analysis populations defined above based on the protocol deviations entered in the database and/or on specific subject classification rules defined in Table 2-1.

Table 2-1 Subject classification based on protocol deviations and non-protocol deviations criteria

| Analysis | Protocol deviations leading to exclusion | Non Protocol deviations leading to exclusion |
|----------|--|--|
|----------|--|--|

| | | |
|------------|-----------------------------|---|
| FAS | No written informed consent | None |
| Safety Set | No written informed consent | No dose of any component of study treatment |
| [REDACTED] | [REDACTED] | [REDACTED] |
| [REDACTED] | [REDACTED] | [REDACTED] |

Withdrawal of Informed Consent

Any data collected in the clinical database after a subject withdraws informed consent from all further participation in the study will not be included in the analyses. The date on which a subject withdraws consent is recorded in the eCRF.

Additional data for which there is a separate informed consent, e.g. biological sample etc., collected in the clinical database without having obtained that consent or after withdrawal of consent will not be included in the analyses.

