2.8.1 Adverse events (AEs)

All information obtained on adverse events will be listed.

Treatment emergent adverse event (TEAE) defined as any adverse event which started on or after the day of first dose of study treatment and before 30 days after last dose of study treatment.

Summary tables for adverse events (AEs) will include only AEs that started or worsened during the on-treatment period. The number (and percentage) of subjects with treatment emergent AEs will be summarized by primary system organ class, preferred term and maximum severity (based on CTCAE grades).

AEs will be summarized by number and percentage of subjects having at least one AE, having at least one AE in each primary system organ class (SOC) and for each preferred term (PT). A subject with multiple occurrences of an AE will be counted only once in the respective AE category. A subject with multiple CTCAE grades for the same preferred term will be summarized under the maximum CTCAE grade recorded for the event. AEs will be assessed according to the Common Terminology Criteria for Adverse Events (CTCAE) version.

All AEs reported in the AE eCRF page will be listed along with the information collected on those AEs, e.g. toxicity grade, relationship to study treatment, outcome, action taken etc. AEs

that started during the pre-treatment, on-treatment, post-treatment and after the overall safety period will be flagged.

Separate summaries will be provided for study treatment related adverse events, death, serious adverse events, non-serious adverse events, adverse events leading to treatment discontinuation, and adverse events leading to dose adjustment by primary system organ class and preferred term.

Selected summaries of adverse events will be produced for the overall safety period. All deaths (on-treatment and post-treatment) will be summarized.

All AEs, deaths, and serious adverse events (including those from the pre- and post-treatment periods) will be listed and those collected during the pre-treatment, post-treatment and overall safety period will be flagged. Subjects who are having AE after transplantation or antineoplastic therapies will be listed & flagged.

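### A protocol note takes participants who stop sabatolimab for transplant out of the safety set, and the SAP does not say whether the note applies, so the primary AE numerator is ambiguous

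*Protocol*

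**What the plan says.** Protocol 12.4.1 makes safety primary: "The variables for the primary analysis are incidence and severity of AEs and SAEs, and changes in laboratory values and vital signs". Protocol 12.1.2 defines the population by exposure alone: "The Safety Set includes all patients who received at least one dose of study medication".

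Protocol 12.5.2.1 sets the main counting window: "on-treatment period: from day of first dose of study medication to last dose of study medication and up to 30 days after last dose". A note in the same list then says that patients who stop MBG453 to receive a transplant leave the set: "they will not be included in the safety set (post discontinuation) and only be followed up for" items that are partly redacted and end with transplant-related mortality.

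SAP 2.2 has its own definition: "The Safety Set includes all subjects who received at least one dose of any component of the study treatment (MBG453 + HMA". SAP Table 2-1 allows exclusion from this set only for missing consent or no dose. SAP 2.8 and 2.8.1 count treatment-emergent AEs to 30 days after last dose and add AE and SAE tables for an overall safety period reaching 150 days after MBG453. Neither section makes an exception for transplant. On transplanted subjects, SAP 1.1 says "However, they may continue into the extension phase for safety", and SAP 2.8.1 says "Subjects who are having AE after transplantation or antineoplastic therapies will be listed & flagged".

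SAP section 1 also states that, except where it specifies something different, "the statistical methodologies including the analysis sets, analysis models, algorithms, and conventions are following the Oncology study amended protocol". SAP section 4, on changes from the protocol's analyses, has two redacted bullets and one legible bullet, which concerns subgroup and sensitivity analyses.

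**The concern.** The note makes membership of the safety population depend on something that happens after treatment starts. It also starts the exclusion when MBG453 is discontinued, not at transplant. AEs between the last antibody dose and the transplant, before any transplant toxicity can confuse attribution, would go uncounted although they fall in the window that the protocol itself calls on-treatment.

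This bears on the primary question. Events soon after an immune-modulating antibody in patients going on to transplant are part of the combination's safety profile, and a footnote to the protocol's assessment schedule says more data are needed on such patients. If earlier AEs stay in and later ones drop out, tabulated incidence can only fall.

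The second problem is that the documents allow two numerators. A programmer who applies the protocol note and one who applies the SAP's Safety Set could both claim to follow the plan.

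**Working it through.** **1. Texts side by side**

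| Source | Transplanted participants after MBG453 stops |
|---|---|
| Protocol 12.5.2.1, note | Out of the safety set |
| Protocol 12.1.2 | In: any dose qualifies |
| Protocol 3 and 6.5.1 | All participants followed for AEs, no transplant exception |
| Protocol 9.1.5 | HSCT patients enter the extension phase, followed for efficacy and safety |
| SAP 2.2 and Table 2-1 | In: excluded only for no consent or no dose |
| SAP 2.8 and 2.8.1 | AEs to last dose plus 30 days counted for every subject |

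The note stands alone against all the other entries.

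**2. Length of the dropped window**

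- Main AE tables: these take only events that start or worsen on treatment. If both drugs stop together, at most 30 days per participant are dropped, counted from the last dose.
- If the HMA continues after MBG453, on-treatment time runs on and the loss exceeds 30 days. Protocol 3 stops only MBG453 for transplant, whereas Protocol 9.1.1 and SAP 1.1 stop study treatment. These passages must be reconciled.
- Overall-safety-period summaries: up to 150 days after MBG453.

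**3. The plan's own precision figure**

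Inputs from Protocol 12.7: expected incidence p = 0.30, half-width d = 0.10, two-sided 95%.

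n = 1.96² × p(1 − p)/d² = 3.8415 × 0.21/0.01 = 80.67, rounded up to 81. This reproduces. With 10% drop-out (SAP section 3), 81/0.90 = 90, which also reproduces.

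At the 39 enrolled, the half-width is 1.96 × √(0.21/39) = 0.144, or 14.4 points.

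**4. Size of the effect at N = 39**

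Each participant counts once per AE term. The note therefore changes a term's incidence only for someone whose sole occurrence falls in the dropped window. With k such participants kept in the denominator, the drop is k/39. The documents do not give the number transplanted, so k is an assumption:

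| k | Drop in incidence (points) |
|---|---|
| 1 | 2.6 |
| 2 | 5.1 |
| 4 | 10.3 |
| 8 | 20.5 |

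Illustration with k = 4: 12/39 = 30.8% (exact 95% CI 17.0 to 47.6) becomes 8/39 = 20.5% (9.3 to 36.5). If the four also left the denominator, the result would be 8/35 = 22.9%. Neither document states the denominator. Keeping them in is the natural reading, because their earlier AEs remain.

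**The case against.** The strongest reply is that the SAP already does the right thing. The protocol leaves detailed methods to the SAP, the SAP yields to the protocol only where it is silent, and on the Safety Set it is not silent. On that reading the planned tables lose nothing and only a stray protocol sentence remains. This stands in part: it is the better reading of the SAP, so a flat statement that the plan deletes these AEs from the primary tables would go too far. It does not remove the ambiguity. The SAP never mentions the note, and a reader could equally treat the note as a protocol convention about the set that the SAP inherits.

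A reader might also infer three stronger things that the documents do not support.

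- *The SAP only lists and flags AEs after transplant.* Its sentence says that they are listed and flagged. Nothing there takes them out of the tables.
- *Each transplanted participant costs 150 days of primary AE data.* Days 31 to 150 are outside the main tables for everyone; they enter only the overall-period summaries and the separate follow-up description.
- *Incidence is understated by 5 to 13 points.* That is 2/39 to 5/39. It assumes the transplant count and needs every one of those participants to have a sole occurrence of the same term in the window. Protocol 5.1 enrols patients unsuitable for immediate transplant, so the count may be small.

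Excluding AEs after transplant could also be deliberate, to avoid charging transplant toxicity to the combination. That would be arguable for events after the transplant, but the note starts earlier. Finally, the redacted words in the note and the two redacted bullets in SAP section 4 may bear on this, and their absence is not held against the plan.

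**Conclusion.** The point holds as an unreconciled contradiction over the primary AE numerator. The protocol note, if applied, lowers tabulated AE incidence within the protocol's own on-treatment window and conflicts with four other protocol sections and with the SAP. If the SAP's definitions govern, nothing is lost. The plan should say which.

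The size is bounded, not known: at most 2.6 points per AE term for each participant whose only occurrence falls in the dropped window. This assumes 39 in the denominator; the transplant count would be needed for a total. AEs before discontinuation are unaffected, and both documents list all AEs, so the loss is mainly in tabulated incidence. Maximum grade could also be understated if an event worsens after discontinuation. It cannot be concluded that the SAP silently abandoned the note, because only part of section 4 is legible.

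**What to change.** State in SAP 2.2 and 2.8, record in SAP section 4, and repeat in the CSR, that the transplant note in Protocol 12.5.2.1 is not applied. Participants who go to transplant stay in the Safety Set, and their collected AEs count in the on-treatment and overall safety periods. Add a supplementary table that separates AEs after HSCT, so that transplant toxicity can be seen apart.

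Add a footnote on collection. Protocol 10.1.1 limits collection to AEs suspected to be related once new antineoplastic medication starts. If conditioning counts as such medication, or if sites took the note as an instruction on what to follow, unrelated AEs may not have been recorded.

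The current SAP addendum is dated after database lock, so a SAP and CSR statement is more practical than a protocol amendment. The cost is a few lines, one table and a footnote, using data already collected. The downside is that some transplant-related AEs enter the main tables, which the supplementary table makes visible.

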### 12.5.2.2 Adverse events (AEs)

All information obtained on adverse events will be displayed by treatment and participant.

Summary tables for adverse events (AEs) will include only AEs that started or worsened during the on-treatment period. The number (and percentage) of participants with treatment emergent AEs will be summarized by primary system organ class, preferred term and maximum severity (based on CTCAE grades). Separate summaries will be provided for study medication related adverse events, deaths, serious adverse events, adverse events leading to treatment discontinuation, and adverse events leading to dose adjustment. The number (and percentage) of participants with adverse events will be summarized by primary system organ class, preferred term and maximum severity.

Separate summaries will be provided for study medication related adverse events, death, serious adverse events, adverse events leading to treatment discontinuation, and adverse events leading to dose adjustment.

The incidence of adverse events will be summarized by system organ class and or preferred term, severity (based on CTCAE grades), type of adverse event, relation to study treatment.

Serious adverse events and non-serious adverse events will be tabulated.

Selected summaries of adverse events will be produced for the overall safety period. All deaths (on-treatment and post-treatment) will be summarized.

All AEs, deaths, and serious adverse events (including those from the pre- and post-treatment periods) will be listed and those collected during the pre-treatment, post-treatment and overall safety period will be flagged.

### **12.5.2.3 Laboratory abnormalities**

Grading of laboratory values will be assigned programmatically as per NCI CTCAE version 5.0. The calculation of CTCAE grades will be based on the observed laboratory values only, clinical assessments will not be taken into account.

CTCAE Grade 0 will be assigned for all non-missing values not graded as 1 or higher. Grade 5 will not be used.

For laboratory tests where grades are not defined by CTCAE v5, results will be categorized as low/normal/high (or other project-specific ranges, if more suitable) based on laboratory normal ranges.

The following summaries will be generated separately for hematology and biochemistry tests:  
For laboratory tests where grades are defined by CTCAE v5

- Worst post-baseline CTCAE grade (regardless of the baseline status). Each patient will be counted only once for the worst grade observed post-baseline.
- Shift tables to compare baseline CTCAE grades to the worst on-treatment grade

For laboratory tests where grades are not defined by CTCAE v5

- Shift tables using the low/normal/high/low and high (or project specific) classification to compare baseline to the worst on-treatment value.

Listing of all laboratory data with values flagged to show the corresponding CTCAE v5 grades if applicable and the classifications relative to the laboratory normal ranges will be presented.

### **12.5.2.4 Other safety data ECG**

A 12-lead ECG including PR, QRS, QT, QTcF, QTcB and RR intervals will be obtained for each patient during the study.

As appropriate, the number and percent of patients with notable ECG value will be tabulated by category. In addition, a listing of patients with at least one notable ECG value will be produced.

## **12.6 Interim analyses**

As appropriate, interim analyses may be performed for publication or any regulatory purpose. The study primary analysis will be by 12 months post last patient first treatment and a CSR will be written. Additional Final Analyses maybe performed when all patients complete the extension phase and safety follow up. In this case, the final CSR will be written.

## **12.7 Sample size calculation**

This is an open label, non-randomized, single-arm combination study to assess safety and efficacy of MBG453 (sabatolimab) given with HMAs of investigator's choice (IV/ SC/ Oral). The primary objective of the study is to assess safety profile of this combination drug by 12 months.

Given the above expected incidence rates of AEs with the combination (Table 1-3), a sample size of 81 evaluable patients was estimated based on a two sided 95% confidence interval for an incidence rate of an AE using the large sample normal approximation that will extend 0.10 from the observed incidence rate of an AE (precision or margin of error of 10%) for an expected incidence rate of 30%.

Novartis has decided to permanently halt recruitment based on a reevaluation of the development strategy for sabatolimab. Patients who are currently on study treatment or in follow-up will be continue per the protocol. At the time of this amendment, 39 patients have been enrolled into the study.

# **13 Ethical considerations and administrative procedures**

## **13.1 Regulatory and ethical compliance**

This clinical study was designed, shall be implemented and reported in accordance with the ICH Harmonized Tripartite Guidelines for Good Clinical Practice, with applicable local regulations (US Code of Federal Regulations Title 21), and with the ethical principles laid down in the Declaration of Helsinki.

## **13.2 Responsibilities of the investigator and IRB/IEC/REB**

Before initiating a trial, the investigator/institution must obtain approval/favorable opinion from the Institutional Review Board/Independent Ethics Committee (IRB/IEC) for the trial protocol, written informed consent form, consent form updates, participant recruitment procedures (e.g. advertisements) and any other written information to be provided to participants. Prior to study

start, the investigator is required to sign a protocol signature page confirming his/her agreement to conduct the study in accordance with these documents and all of the instructions and procedures found in this protocol and to give access to all relevant data and records to field monitors, auditors, Novartis Quality Assurance representatives, designated agents of Novartis, IRBs/IECs, and regulatory authorities as required. If an inspection of the clinical site is requested by a regulatory authority, the investigator must inform Novartis immediately that this request has been made.

### **13.3 Informed consent procedures**

Eligible patients may only be included in the study after providing written (witnessed, where required by law or regulation), IRB/IEC/REB-approved informed consent.

Informed consent must be obtained before conducting any study-specific procedures (i.e., all of the procedures described in the protocol). The process of obtaining informed consent must be documented in the patient source documents. The date when a patient's Informed Consent was actually obtained will be captured in their eCRFs.

Novartis will provide to investigators, in a separate document, a proposed informed consent form (ICF) that is considered appropriate for this study and complies with the ICH GCP guideline and regulatory requirements. Any changes to this ICF suggested by the investigator must be agreed to by Novartis before submission to the IRB/IEC/REB, and a copy of the approved version must be provided to the Novartis monitor after IRB/IEC/REB approval.

Women of child bearing potential must be informed that taking the study medication may involve unknown risks to the fetus if pregnancy were to occur during the study and agree that in order to participate in the study they must adhere to the contraception requirement for the duration of the study. If there is any question that the patient will not reliably comply, they must not be entered in the study.

